6. STUDY POPULATION

6.1. **Subject Disposition**

Subject disposition information will be summarized and will include number of subjects screened, number of subjects included in the ITT population, the number of subjects completing the treatment phase of the study, the number of subjects completing the study through follow-up and primary reason for discontinuation.

6.2. **Protocol Deviations**

Protocol deviations will be summarized by deviation category (major, minor). Additionally, protocol deviations will be presented in a data listing.

6.3. Eligibility

Participants not fulfilling the eligibility criteria will be presented in a data listing.

CONFIDENTIAL Page 11/21

6.4. Demographic and Baseline Characteristics

Demographic variables include age, sex, ethnicity, race, and Fitzpatrick skin type. Age will be reported on the CRF and will be based on age at time of signing informed consent.

Baseline characteristics (head and neck reg	gion) include	Physician Global
Assessment (PGA) for the target lesion,		

Unless otherwise noted, baseline is defined as the last non-missing value recorded before the first dose of study drug. Unscheduled visits will be used in the determination of baseline values, when applicable.

6.5. Medical History

Medical history will be coded using the Medical Dictionary for Regulatory Activities (MedDRA, version 26.0). The summary will show the system organ class (SOC) and preferred terms (PT) ordered alphabetically by SOC and descending PT frequency. The corresponding data listing by participant will be ordered by start date, then alphabetically by SOC and PT.

Psoriasis history in the head and neck region will be summarized by duration of disease (<5 years, 5-10 years, >10 years) and by location of target lesion.

6.6. Prior and Concomitant Therapy

Prior and concomitant medication verbatim terms will be mapped to Anatomical/Therapeutic/Chemical (ATC) class and preferred names using the WHODrug global dictionary (Version B3 01MAR2023).

Prior (within the 30 days before screening, and with stop dates prior to first dose of study drug) and concomitant (ongoing or with stop dates on or after first dose of study drug) medications will be listed by subject. If the medication is ongoing or the stop year is missing, the medication will be considered as received for the entire duration of the study.

To distinguish prior vs concomitant medications, the following rules for stop dates will apply:

- If only year was recorded, and it is before Baseline, it is a prior medication; if year is same or after Baseline, it is assumed to be a concomitant medication.
- If day is missing, but month and year are before Baseline, it is a prior medication; if month and year are the same as Baseline, it is assumed to be a concomitant medication; if month and year are after Baseline, it is a concomitant medication.
- If start date is after Baseline, it is a concomitant medication regardless.

Prior and concomitant medications will be summarized separately by WHO ATC 2 and preferred name. Subjects may have more than 1 medication per ATC 2 and preferred name. At each level of subject summarization, a subject is counted once if he/she reported 1 or more medication at that level. Frequencies and percentages of prior and concomitant medications will be ordered alphabetically by ATC class and descending preferred name. The corresponding data listing by

CONFIDENTIAL Page 12/21

Dermavant Sciences, Inc. DMVT-505-4002

Statistical Analysis Plan, v1.0 24JUL2023

participant will be ordered by start date of administration then alphabetically by ATC Class and preferred name.

CONFIDENTIAL Page 13/21

7. EFFICACY ANALYSES

All efficacy analyses will be performed based in the ITT population.

7.1. Efficacy Endpoints

The primary efficacy endpoint is the percentage of participants who achieve a PGA (target lesion) score of clear (0) or almost clear (1) with a \geq 2-grade improvement from Baseline at Week 12.

The secondary efficacy endpoint is the time to achieve a PGA (target lesion) score of 0 or 1 with $a \ge 2$ -grade improvement from Baseline.

CONFIDENTIAL Page 14/21

Dermavant Sciences, Inc. DMVT-505-4002

Statistical Analysis Plan, v1.0 24JUL2023

7.2. Efficacy Analyses

Categorical endpoints will be summarized by presenting counts and percentages of subjects in corresponding categories. Percentages for missing values are omitted and do not account for the percent calculation of other categories. 95% confidence intervals will be presented.

Continuous endpoints will be summarized by presenting the number of observations, means, standard deviations, medians, minimums, maximums, and 95% confidence intervals.

The Kaplan-Meier product limit method will be used to estimate the median time to achieving a target lesion PGA score of 0 or 1 with a \geq 2-grade improvement from Baseline,

Categorical endpoints include:

• Percentage of participants who achieve a PGA (target lesion) score of clear (0) or almost clear (1) with a \geq 2-grade improvement from Baseline

- •
- •
- •

7.3.

Dermavant Sciences, Inc. Statistical Analysis Plan, v1.0 DMVT-505-4002 24JUL2023

CONFIDENTIAL Page 16/21

8. SAFETY ASSESSMENTS

8.1. Extent of Exposure

The following exposure and compliance parameters will be summarized descriptively by treatment:

- Total number of days exposed, defined as date of last dose of study drug date of first dose of study drug + 1.
- Number of doses administered will be calculated from the in-clinic dose at Baseline, the subject dose diary and number of missed doses from the summary of missed doses form. If a subject is exposed to study drug for more than 1 day, and returns no diary records, then the total number of doses is regarded to be missing. Otherwise, for any day for which there is no diary record, it is assumed that no study drug was administered at home.
- Percent compliance will be calculated as the (Number of Doses Administered) / (Number of Days Exposed) * 100.
- Subject compliance, defined as ≥80% compliance while enrolled in the study. If the percentage of study medication compliance cannot be computed, the subject is assumed to be less than 80% compliant.

A subject will be compliant with the dosing regimen if they applied \geq 80% of the expected doses. Expected number of doses is based on length of time enrolled in the treatment-phase of the study.

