6.6 Dose Modification

Dosing may be temporarily interrupted if deemed necessary by the Investigator for management of AEs.

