7.1 Discontinuation of Study Intervention

In rare instances, it may be necessary for a participant to permanently discontinue study product. If study product is permanently discontinued, the participant should, if at all possible, remain in the study to be evaluated for safety. See the SoA for data to be collected at the time of discontinuation of study product and follow-up and for any further evaluations that need to be completed.

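### Do the two descriptions of the 80% compliance flag in SAP 8.1 conflict enough to need a change?

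*SAP*

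**What the plan says.** SAP 8.1 (Extent of Exposure) has four relevant statements.

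- Days exposed: "Total number of days exposed, defined as date of last dose of study drug date of first dose of study drug + 1". The minus sign between the two dates is missing from the extracted text; the meaning is clear.
- Percentage: "Percent compliance will be calculated as the (Number of Doses Administered) / (Number of Days Exposed) * 100".
- Flag, with the threshold at 80% or more: "compliance while enrolled in the study. If the percentage of study medication compliance cannot be computed, the subject is assumed to be less than 80%".
- Closing paragraph: a participant is compliant after applying at least 80% of expected doses, and "Expected number of doses is based on length of time enrolled in the treatment-phase of the study".

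The Protocol allows dosing and participation to end at different times. Section 7.1 describes permanent discontinuation of product as a rare event and adds: "If study product is permanently discontinued, the participant should, if at all possible, remain in the study to be evaluated for safety". SAP 6.1 reports separately "the number of subjects completing the treatment phase of the study, the number of subjects completing the study through follow-up". No visible text states whether the treatment phase of a participant who has stopped the cream ends at the last dose or at the Week 12 visit.

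**The concern.** One flag appears to have two denominators. The percentage uses the interval from first to last dose. The flag bullet speaks of "compliance while enrolled in the study", and the closing paragraph of time in the treatment phase. Nothing states outright which prevails.

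For someone who stops the cream early and stays for follow-up, the first denominator ends when dosing ends, while the second might run on to Week 12. Two programmers could then classify that person differently, and the reported share with at least 80% compliance would depend on which sentence was coded. The days-exposed version is also the flattering one: someone who stops in Week 2 without missing a dose is 100% compliant. The Protocol's rationale names poor adherence as a weakness of existing topical treatments in this region, so a reader may look at this figure.

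**Working it through.** The plan states no compliance result, so there is no figure to reproduce. The check compares the two descriptions.

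**Inputs.** Once-daily dosing (Protocol 8.1.4), so one expected dose per day. Treatment for up to 12 weeks (SAP 3.1), so T = 84 days, or 85 if Day 85, the Week 12 target day in SAP 5.3, is counted. Planned N = 30 (SAP 4).

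**Formulas**, with first dose on Day 1:
- A = doses / day of last dose
- B = doses / T, taking the treatment phase to run to Week 12

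**Stops the cream, stays enrolled, T = 84**

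| Last dose | Missed before | A | B | Same class? |
|---|---|---|---|---|
| Day 14 | 0 | 14/14 = 100% | 14/84 = 16.7% | No |
| Day 40 | 0 | 40/40 = 100% | 40/84 = 47.6% | No |
| Day 56 | 5 | 51/56 = 91.1% | 51/84 = 60.7% | No |
| Day 67 | 0 | 67/67 = 100% | 67/84 = 79.8% | No |
| Day 68 | 0 | 68/68 = 100% | 68/84 = 81.0% | Yes |
| Day 74 | 7 | 67/74 = 90.5% | 67/84 = 79.8% | No |

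With no missed doses, the classes differ for any last dose up to Day 67. The limit is the same for T = 85: 67/85 = 78.8% and 68/85 = 80.0%. As the last row shows, missed doses can push the conflict somewhat later. B never exceeds A, so the disagreement runs in one direction only.

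**Where the descriptions agree**
- Dosing to the end of treatment: 84 days with 10 missed gives 74/84 = 88.1% under both (74/85 = 87.1% for B if T = 85, same class).
- Leaving the study on stopping: last dose Day 40, exit visit assumed on Day 43, gives 100% and 40/43 = 93.0%, same class.
- Under 80% adherent before stopping: non-compliant under both.
- Interrupted and then resumed to the end of treatment (Protocol 6.6: "Dosing may be temporarily interrupted if deemed necessary by the Investigator for management of AEs"): the gap lies between first and last dose, so both denominators contain it. For example, 40 doses to Day 40 and one more on Day 84 gives 41/84 = 48.8% under both.
- Treatment phase read as ending at the last dose: T equals the day of last dose, so B = A for everyone.

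**Reading the text.** The percentage bullet is the only formula in the section. The flag bullet says what to do when the percentage cannot be computed, and the only percentage defined is the one in the bullet above it. The closing paragraph supplies neither a formula nor an end date, and it says treatment phase, not study. Protocol 7.1 keeps people who have stopped in the study for safety evaluation; it does not place them in the treatment phase.

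**Size.** Each discordant participant moves the compliant share by 1/30 = 3.3 points. The documents give no expected number. Assuming 1 to 3 gives 3.3 to 10.0 points, but three in 30 is hard to square with the Protocol calling permanent discontinuation rare. Each must also stay enrolled, have been at least 80% adherent up to stopping, and stop by about Day 67.

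**The case for a change.** The strongest case for a change is that the inconsistency is in the current SAP text and the Protocol foresees the participants it touches. Protocol 8.4.5 treats stopping product and leaving the study as alternatives, and SAP 8.2 tabulates adverse events leading to each separately. Being enrolled is ordinarily a matter of participation, not dosing, and if the treatment phase simply ended at the last dose, the closing paragraph would add nothing. One sentence would settle it without new data.

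The drafting criticism stands: 8.1 is loosely worded, and the documents do not say outright which denominator is meant. The case for a particular repair does not stand. Setting the denominator to run to Week 12 or withdrawal would merge adherence while on treatment with persistence on treatment. A participant taken off the cream for an adverse event or a pregnancy would be counted as non-compliant after following every instruction. Persistence is already shown by days exposed (SAP 8.1), disposition (SAP 6.1) and adverse events leading to discontinuation (SAP 8.2).

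The repair would also bring its own boundary question. Someone with 68 doses, the last on Day 84, and a Week 12 visit assumed on Day 86 would go from 68/84 = 81.0% to 68/86 = 79.1% and change class merely because of the visit date. Defining where the treatment phase ends would avoid that choice of denominator, but it only supplies detail a programmer can settle from the formula already given.

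**Conclusion.** No change is needed. Section 8.1 uses two wordings for one flag, and they can give opposite classes for a participant who stops the cream for good by about Day 67, with few earlier misses, and stays enrolled. That happens only if the undefined treatment phase is read as continuing after the last dose. The natural course is to apply the one stated formula to both the percentage and the flag.

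If the other reading were coded, the effect would be 3.3 points per affected participant in a descriptive table, with zero or one participant plausible. That count is a judgement resting on the Protocol's description of permanent discontinuation as rare, not on a figure in the documents. ITT is the only analysis set, no visible efficacy analysis uses the flag, and SAP 5.1 lists individual and derived data by participant, so any odd case can be seen. The primary responder percentage, the time-to-response estimate and the safety tables are the same on either reading.

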8.2. Adverse Events

All AE summaries will be restricted to TEAEs, which are defined as those AEs that occurred after dosing and those pre-existing AEs (prior to first application of study treatment) that worsened during the study. If it cannot be determined whether the AE is treatment emergent due to a partial onset date, then it will be counted as TEAE. Verbatim terms in the eCRFs will be mapped to SOCs and PTs using MedDRA (Version 26.0).

Imputation of start and end dates of AEs

To calculate duration of AEs, the following rules will be used where applicable to impute partial or completely missing start dates or end dates:

- If only the day is missing for a start date, the 1st of the month will be imputed. If the new estimated date falls before the date of first dose, while the known month and year match the month and year of the first dose, the date of first dose will be used as the new estimated date. The AE will be considered as a treatment-emergent AE (TEAE).
- If only the day is missing for an end date, the last day of the month will be imputed. If the new estimated date falls after the date of last study visit, the date of last study visit will be used as the new estimated date. Last study visit is defined as the Week 13 visit.

CONFIDENTIAL Page 17/21

- If both the day and the month are missing for a start date or end date, no imputation will be used, and the duration will not be calculated. However, if the year of start is the same or greater than the year of the first dose date, the AE will be considered as a TEAE.
- If the start date or end date is completely missing, duration will not be calculated. However, an event with completely missing start date will be considered as a TEAE.

Imputation of missing relationship and/or missing severity

If relationship to treatment is missing, the event will be conservatively treated as related to study drug.

If severity is missing and the AE is reported as serious and fatal, severity will be imputed as CTCAE=5. If severity is missing and the AE is reported as serious and not fatal, severity will be imputed as CTCAE=4. If severity is missing and the AE is not reported as serious, severity will be imputed as CTCAE=3.

All AEs will be listed by subject, detailing the verbatim term given by the investigator, the SOC, PT, onset date and time, end date and time, duration (days), common terminology criteria for adverse events (CTCAE) grade, outcome, relationship to study drug, action taken with study drug, other action taken to treat the event, seriousness, and criteria for seriousness. Serious AEs (SAEs), TEAEs related to study drug, TEAEs leading to study drug discontinuation, and TEAEs leading to study discontinuation will also be listed separately.

All AE will be summarized using frequency counts and percentages:

- Any TEAEs
- Related TEAEs
- TEAEs leading to study treatment discontinuation
- TEAEs leading to discontinuation from study
- Any Serious TEAE (non-Fatal)
- Any Serious TEAE (All)
- Death
- Treatment-related Serious TEAE
- Serious TEAE leading to study treatment discontinuation
- Serious TEAE leading to discontinuation from study

TEAEs will be ordered alphabetically by MedDRA SOC and by descending PT frequency. At each level of summarization, a subject will be counted once if he/she reported one or more events. The maximum severity of TEAEs and strongest relationship to study drug will be summarized in a similar manner. For summaries of relationship to study drug, a subject will be classified according related or not related. For summaries of TEAE CTCAE grade, a subject will be classified according to the worst grade.

CONFIDENTIAL Page 18/21

Dermavant Sciences, Inc.Statistical Analysis Plan, v1.0DMVT-505-400224JUL2023

8.3.

CONFIDENTIAL DMVT-505-4002_SAP_v1.0.docx

[figure not shown]

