8.4.1 Time Period and Frequency for Collecting AE and SAE Information

All AEs and SAEs will be collected from the signing of the ICF until the final visit at the time points specified in the SoA (Section 1.3).

All SAEs will be recorded in the EDC and reported on the required form to the Sponsor or designee immediately and under no circumstance should this exceed 24 hours, as indicated in [Appendix 3](#). The Investigator will submit any updated SAE data to the Sponsor or designee within 24 hours of it being available.

Investigators are not obligated to actively seek information on AEs or SAEs after conclusion of the study participation. However, if the Investigator learns of any SAE, including a death, at any time after a participant has been discharged from the study, and the Investigator considers the event to be reasonably related to the study product or study participation, the Investigator must promptly notify the Sponsor.

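### SAP 8.2 can class an adverse event as treatment-emergent although its recorded end date is before first dose, because three start-date rules do not check the end date

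*SAP*

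**What the plan says.** Protocol 8.4.1 starts AE collection before treatment: "All AEs and SAEs will be collected from the signing of the ICF until the final visit". SAP 8.2 restricts all AE summaries to TEAEs. It defines these as events occurring after dosing, plus events already present before the first application that got worse. It adds a general default: "If it cannot be determined whether the AE is treatment emergent due to a partial onset date, then it will be counted as TEAE".

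The date bullets that follow in SAP 8.2 contain these rules:

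- Day of start missing, same month and year as first dose: "the date of first dose will be used as the new estimated date", and the event is a TEAE.
- Day and month of start missing: the event is a TEAE "if the year of start is the same or greater than the year of the first dose date"; no duration is calculated.
- Start completely missing: "an event with completely missing start date will be considered as a TEAE"; no duration is calculated.
- Day of end missing: the last day of the month is imputed and capped at the last study visit. "Last study visit is defined as the Week 13 visit".

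**The concern.** An event with a recorded end before first dose did not occur after dosing, and it cannot have worsened under treatment. It therefore meets neither limb of the TEAE definition. Each of the three start-date rules nevertheless assigns TEAE status from the start date and the first-dose date alone. The plan then gives two answers for the same record, depending on whether the programmer follows the definition or the bullets.

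What is at stake is the count in the TEAE tables and the credibility of the by-subject AE listing, which prints onset, end and duration. The end-date cap has a smaller gap: it refers to a visit that a participant who leaves the study early does not have.

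**Working it through.** There is no planned figure to reproduce. The check is to apply the rules literally to test records.

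**Inputs from the documents**
- AE collection starts at consent (Protocol 8.4.1).
- Study up to 17 weeks, treatment up to 12, follow-up up to 1 (SAP 3.1). That leaves up to 17 − 12 − 1 = 4 weeks before first dose.
- Planned N = 30 (SAP 4).
- Early-termination visits are assigned by study day. The Week 13 window opens after the later of last treatment day + 3 and Day 87 (SAP 5.3).

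**Assumptions**
- First dose is 20 March and, in cases A to C, the recorded AE end is 10 March.
- Duration = end − start + 1. The visible SAP gives no AE duration formula; this one follows the exposure formula in SAP 8.1. Results without the + 1 are also shown.

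**Start-date rules**

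| Case | Recorded start | Imputed start | Status under the bullets | Duration |
|---|---|---|---|---|
| A | completely missing | none | TEAE | not calculated |
| B | year only, same year as first dose | none | TEAE | not calculated |
| C | March, day missing | 20 March | TEAE | 10 − 20 + 1 = −9 days (−10 without the + 1) |

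All three events ended 10 days before exposure.

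For case C in general, let first dose fall on day f of a 31-day month and the recorded end on an earlier day e. Duration is e − f + 1.
- Smallest value: 1 − 31 + 1 = −29.
- Largest value: (f − 1) − f + 1 = 0.
- Without the + 1 the range is −30 to −1.

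The result is never positive.

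**Size in the summaries**
One participant wrongly counted is 1/30 = 3.3 percentage points. SAP 8.2 counts a participant once at each level, so the any-TEAE rate moves only if that participant has no other TEAE.

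**End-date cap**
- For a last treatment day up to Day 84, the later of (day + 3) and 87 is 87. The Week 13 window therefore opens on Day 88, and an earlier termination visit does not map to Week 13.
- Case D: the participant leaves the study on 2 April; the AE starts 1 April and ends in April with the day missing. With no Week 13 visit to cap at, the imputed end is 30 April. That is 30 − 2 = 28 days after last contact, with a duration of 30 days.

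**After the fix below**
- A, B and C are no longer TEAEs.
- C keeps the first-of-month start: 1 to 10 March, 10 − 1 + 1 = 10 days.
- D ends on 2 April: 2 − 1 + 1 = 2 days.

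**The case against.** The strongest defence is that SAP 8.2 opens with the governing definition, and that its general default applies only where treatment-emergence cannot be determined. The bullets are introduced as rules for working out duration. A sensible programmer could treat them as subordinate and leave out an event known to have ended before dosing. This stands in part: it shows that a miscount is not inevitable. It does not remove the problem, because the bullets assign TEAE status without that condition and the default sentence does not mention the end date. The text is inconsistent and needs reconciling. The SAP does use the stop date to separate prior from concomitant medication (SAP 6.6), so the same check on AEs would not be foreign to the plan.

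The points about size stand in full:
- The trigger is narrow: a pre-dose event with an incomplete start but an end known to precede dosing, within about 4 weeks.
- The error over-counts harm, in line with the conservative approach of the section.
- Duration appears only in a listing in the visible text, with the dates beside it.

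A reader might infer more than this, and the documents do not support it:
- That all three rules produce negative durations. Only the day-missing rule does; the other two calculate none.
- That related or Grade 3–4 counts are inflated. That needs relationship or severity to be missing on the same record as well.
- That every participant who stops treatment lacks a Week 13 visit. Protocol 7.1 asks those who stop product to stay in the study if possible. The schedule of activities is not shown, so follow-up after early withdrawal cannot be checked.

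**Conclusion.** The point holds as a drafting conflict with a small effect. Taken literally, three rules in SAP 8.2 count as treatment-emergent an event that the recorded data show ended before first dose, and one of them also gives an impossible duration. Conservatism justifies counting events whose status is unknown, but not events whose status the end date settles.

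The effect is at most 3.3 percentage points per affected participant at N = 30, and in the any-TEAE row only where that participant has no other TEAE. The number of such participants is not given in the documents; I assume it is low (0 to 2). The −9 days rests on the assumed duration formula, but the absence of any positive value does not. The efficacy endpoints are untouched. The documents do not support concluding that the safety profile would be materially distorted.

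The Week 13 cap is a real but lesser gap, confined to participants who leave the study early. The 28-day overshoot in case D comes from an exit at the start of a month and is not typical.

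**What to change.** Place one sentence before the three start-date rules: *If the known or latest possible end date of the AE is before first dose, the event is not a TEAE, and an imputed start date may not be later than a known end date.* Events with no end date, or with a partial end date that could fall on or after first dose, stay TEAEs as now.

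Minor addition: define the last study visit used for the cap as the participant's actual last visit or contact (Week 13 or early termination), with the capped date never earlier than the AE start date or the first day of the recorded end month. That limit is needed because Protocol 8.4.3 follows SAEs until they resolve or stabilise. An SAE recorded as ending in May in a participant last seen on 2 April must not be given an April end date.

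The cost is two sentences in the SAP and a small programming change before database lock. No additional data are needed.
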